7.6 Procedures at the end of the trial

The trial will be closed when all participants have made their final follow-up visit (visit 12), the data collected on randomised participants entered into the database and the database locked. There will be a final monitoring/closeout visit to the clinical site between the last visit and the database lock.

Table 5: Schedule of visits, Immunisations and Assessments

Visit number	1	2		3	4		5	6		7	8		9	10	11	12
Nature of visit	Screen	Dosing visit	Safety call	Safety visit	Dosing visit	Safety call	Safety visit	Dosing visit	Safety call	Safety visit	Dosing visit	Safety call	Safety visit	Final safety visit	Follow up to assess response	Follow up to assess response
Week ⁶	-6	0	0+1d	1	4	4+1d	5	8	8+1d	9	20	20+1d	21	22	24	44
Visit window (days)	N/A	N/A	Vaccine 1+3d	-3d+7d	±3d	Vaccine 2+3d	-3d+7d	±3d	Vaccine 3+3d	-3d+7d	±3d	V4+3d	-3d+3d	-3d+3d	-3d+3d	-14d to +14d
Informed consent	X															
Demographics/ Medical history/ screening exam	X															
General exam	X	X		(X)	(X)											
ECG	X															
Vital signs	X	X ⁷		X	X ⁷		X	X ⁷		X	X ⁷		X	X		
Inspection of administration sites	X	X ⁷	X ⁸	X	X ⁷	X ⁸	X	X ⁷	X ⁸	X	X ⁷	X ⁸	X	(X)		
Adverse event and conmeds assessment		X ⁷	X	X	X											
Urine pregnancy test ⁴	X	X			X			X			X				X	
Routine safety bloods ¹	X	X		X	X		X	X		X	X		X	X		
Urinalysis	X	X		X	X		X	X		X	X		X	X		
HIV test ²	X	(X)			(X)			(X)			(X)				X	(X)
HBV, HCV, syphilis, urine for chlamydia, and gonnorrhoea ⁴	X															
Other gonnorrhoea and chlamydia tests ⁴	(X)															
Blood for serum – Immunogenicity		X			X		X	X		X	X		X	X	X	X
Mucosal sampling		X									X			X		

Blood for PBMC – Immunogenicity		X			X			X			X			X	X	X	X
Immunisation⁵		V1			V2			V3			V4						
Tolerability questionnaire ⁹		X			X			X									
Diary card ³				X			X			X			X				

X means mandatory, (X) means if clinically indicated

1 The parameters are detailed in section 7.2.3

2 At each dosing visit clinic staff will determine whether the risk status for HIV has changed and repeat the test if necessary

3 Diary card given to subjects at each vaccination visit, and reviewed with subject at time-points indicated

4 Additional HIV/STI and pregnancy tests will be performed if indicated by a change in risk status or menstrual history respectively

5 Immunisation should be after completion of the other procedures scheduled for that visit except for the AE assessment and injection site inspection which will be conducted before and after each immunisation

6 After the first vaccination the timing of all visits is determined by the date of the preceding vaccination

7 Pre-dose and again at 10 (+/-2) min and 60 (+/-10) min post-dose; subjects are free to leave after the 60 min post-dose assessment unless otherwise indicated by AEs etc.

8 Volunteer invited back to clinic for assessment if reporting grade 3 AE or above

9 The tolerability questionnaire should be completed post-vaccinations 1–3 only

8. SAFETY REPORTING

UK clinical trials regulations require that both investigators and sponsors follow specific procedures when notifying and reporting adverse events/reactions in clinical trials. These procedures are described in this section of the protocol. **Section 8.1** lists definitions, **section 8.2** describes details of the responsibilities of the institutions/investigators.

8.1 Definitions

The definitions of the EU Directive 2001/20/EC Article 2 based on the principles of ICH GCP apply to this protocol. These definitions are given below:

Adverse event

Any untoward medical occurrence in a subject to whom a medicinal product has been administered, including occurrences which are not necessarily caused by or related to that product.

The investigator will use the following criteria when deciding whether to report a laboratory parameter that falls outside the normal range according to the local laboratory guidelines as an adverse event:

- The test result is associated with relevant accompanying symptoms
- Additional diagnostic tests or medication are indicated
- As a consequence of the test result, an immunisation is delayed or further immunisations are discontinued
- The investigator considers the result to constitute an adverse event for any other reason

Adverse reaction

Any untoward and unintended response in a subject to an investigational medicinal product which is related to any dose administered to that subject.

'Related' means possibly, probably or definitely as defined below.

All solicited adverse events which start within 7 days of a vaccination will be automatically classified as an adverse reaction.

Unexpected adverse reaction

An adverse reaction, the nature or severity of which is not consistent with the information about the medicinal product in question set out in the Investigator's Brochure.

Serious Adverse Events (SAEs), Serious Adverse Reaction (SARs), Suspected Unexpected Serious Adverse Reactions (SUSARs)

Any adverse event, adverse reaction, or unexpected adverse reaction is considered to be a "serious" if it:

- Results in death
- Is life-threatening
- Requires hospitalisation or prolongation of existing hospitalisation
- Results in persistent or significant disability or incapacity
- Consists of a congenital anomaly or birth defect
- Any other medically important event

Notes:

- **'A threat to life'** refers to an event or reaction in which the patient was at risk of death at the time of the event; it does not refer to an event or reaction which hypothetically might have caused death had it been more severe.

If an AE is serious and unexpected and considered possibly, probably or definitely related to study product according to the classification below then it meets the criteria for a SUSAR and should be reported accordingly.

Relationship to study product

This can be classified as:

Unrelated	adverse events that can be clearly explained by extraneous causes and for which there is no plausible association with study product, or adverse events for which there is no temporal relationship
Unlikely	adverse events that may be temporally linked, but which are much more likely to be due to other causes than study product and which do not get worse with continuing use of product
Possibly	adverse events that could equally well be explained by study product or other causes, which are usually temporally linked and may improve when not using study product but do not reappear when using study product
Probably	adverse events that are temporally linked and for which the study product is more likely to be the explanation than other causes, which may improve when not using study product
Definitely	adverse events that are temporally linked and for which the study product is the most likely explanation, which disappear or decrease when not using study product and reappear when using study product

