7.4.3.2 Urine

- protein, ketones, blood, leukocyte esterase, and nitrites – by dipstick

A urine specimen will be sent to the laboratory if the level of protein, blood, leukocyte esterase or nitrites is considered clinically relevant.

Various local and systemic adverse events are known to be associated with licensed vaccines, and are referred to as '**solicited adverse events**'. These include disturbances in routine laboratory parameters, and are described in **table 2** below.

Information on solicited adverse events will be collected on the day of each immunisation (pre-immunisation, and at 10 and 60 minutes post-immunisation), at a safety call the day after each immunisation and for the following 7 days through a structured interview and examination according to the schedule.

In addition systemic laboratory adverse events will be collected through routine laboratory testing according to the schedule. These will be recorded on the appropriate CRF page.

Participants will also be asked to complete a diary card recording solicited adverse events that start within 7 days of each immunisation.

Table 2: Solicited Adverse Events

Type	Event
Local AEs (immunisation site)	Discomfort Redness Swelling (soft) Induration (hard) Blisters
Systemic Clinical AEs	Abnormally raised temperature Chills Myalgia/flu-like general muscle aches Malaise (excess fatigue) Headache Nausea Vomiting
Systemic Laboratory AEs	Abnormalities in: Creatinine, AST, ALT, alkaline phosphatase, total bilirubin, glucose Hb, total WCC, neutrophils, lymphocytes, platelets

The events will be **graded** according to the study specific toxicity table (see **Appendix 2**).

Relationship to study product, which is defined in **section 8**, will be recorded in the immunisation CRF but not on the diary card, on the assumption that any of these events starting within 7 days of an immunisation are at least possibly related. If the onset is beyond 7 days, the event will be recorded on the adverse event CRF and a relationship determined by the investigator reviewing the event.

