10.2 Endpoints

10.2.1 Primary Endpoints

10.2.1.1 Safety

- Grade 3 or above local solicited adverse event (**Table 2**)
- Grade 3 or above systemic clinical and laboratory solicited adverse event (**Table 2**)
- Any grade of adverse event that results in a clinical decision to discontinue further immunisations
- Any grade of adverse event within 7 days of receiving intradermal and standard intramuscular vaccinations with or without electroporation

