APPENDIX 2: TOXICITY TABLE

Based on systems in use at the MRC CTU, IAVI and NIH Division of AIDS

Abbreviations:	ULN	Upper Limit of Normal	LLN	Lower Limit of Normal
	R _x	Therapy	Req	Required
	Mod	Moderate	IV	Intravenous
	ADL	Activities of Daily Living	Dec	Decreased

For other events not specified in the tables below the severity will be determined according to the US department of health and human services: *Guidance for Industry – Toxicity grading scale for Healthy adult and adolescent volunteers enrolled in Preventative Vaccine Clinical trials.*

<http://www.fda.gov/downloads/BiologicsBloodVaccines/GuidanceComplianceRegulatoryInformation/Guidances/Vaccines/ucm091977.pdf>

LABORATORY PARAMETERS

PARAMETER	GRADE 1 MILD	GRADE 2 MODERATE	GRADE 3 SEVERE	GRADE 4 EXTREME
HAEMATOLOGY				
Hb	10.0-10.9 g/dL	9.0-9.9 g/dL	7.0-8.9 g/dL	<7.0 g/dL
White Blood Count	13.0 – 14.9 x10 ⁹ /l or 2 – 2.5 x10 ⁹ /l	15.0 – 19.9 x10 ⁹ /l or 1.5 – <2.0 x10 ⁹ /l	20.0 – 29.9 x10 ⁹ /l or 1 – <1.5 x10 ⁹ /l	≥30.0 or <1.0 x10 ⁹ /l
Absolute Neutrophils	1.3-1.0 x10 ⁹ /l	<1.0-≥0.75 x10 ⁹ /l	<0.75-≥0.5 x10 ⁹ /l	<0.5 x10 ⁹ /l
Percent neutrophils	>80%	90%	≥95%	---
Lymphocytes	0.7- 0.899 x10 ⁹ /l	0.5-0.699 x10 ⁹ /l	0.35-0.499 x10 ⁹ /l	<0.35 x10 ⁹ /l
Platelets	100 –124.999 x 10 ⁹ /l	50 – 99.999 x 10 ⁹ /l	25 – 49.999 x10 ⁹ /l	<25.0 x10 ⁹ /l
CD4 Count	300-400/mm ³	<300mm ³	<200/mm ³	<100/mm ³
BIOCHEMISTRY				
Potassium				
Hyperkalemia	5.6 – 6.0 meq/L	6.1-6.5 meq/L	6.6-7.0 meq/L	>7.0 meq/L
Hypokalemia	3.0 – 3.4 meq/L	2.5 – 2.9 meq/L	2.0- 2.4 meq/L	<2.0 meq/L
Bilirubin				
Hyperbilirubinemia	>1.25 – 2.0 x ULN	>2.0 – 2.5 x ULN	>2.5 – 5 x ULN	>5 x ULN
Glucose				
Hypoglycaemia	2.3-2.4 mmol/l	2.1-2.2 mmol/l	1.5-2.0 mmol/l	<1.5 mmol/l
Hyperglycaemia nonfasting; no prior diabetes	7.0-10.0 mmol/l	10.1-15.0 mmol/l	15.1-25.0 mmol/l	>25.0 mmol/l
Transaminases				
AST (SGOT)	1.25 – 2.5 x ULN	>2.5 – 5.0 x ULN	>5.0 – 10.0 x ULN	> 10.0 x ULN
ALT (SGPT)	1.25 – 2.5 x ULN	>2.5 – 5.0 x ULN	>5.0 – 10.0 x ULN	> 10.0 x ULN
GGT	1.25 – 2.5 x ULN	>2.5 – 5.0 x ULN	>5.0 – 10.0 x ULN	> 10.0 x ULN
Alk Phos	1.25 – 2.5 x ULN	>2.5 – 5.0 x ULN	>5.0 – 10.0 x ULN	> 10.0 x ULN
Amylase	>1.0 – 1.5 x ULN	>1.5 – 2.0 x ULN	>2.0 – 5.0 x ULN	>5.0 x ULN
Creatinine	130-180 μ mol/l	181-360 μ mol/l	361-720 μ mol/l	>720 μ mol/l
URINALYSIS				
Proteinuria: 24 hour urine	200 mg - 1 g loss/day OR <0.3% OR <3 g/l	1 – 2 g loss/day OR 0.3 – 1.0% OR 3 - 10 g/l	2 – 3.5 g loss/day OR >1.0% OR > 10 g/l	Nephrotic syndrome OR >3.5 g loss/day

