3.1. Primary Endpoints

3.1.1. Safety

Any of the following events occurring between week 0 and week 22 will be included in the analysis:

- Grade 3 or above local solicited adverse event (Table 2)
- Grade 3 or above systemic clinical and laboratory solicited adverse event (Table 2)
- Any grade of adverse event that results in a clinical decision to discontinue further immunisations
- Any grade of adverse event within 7 days of receiving intradermal and standard intramuscular vaccinations with or without electroporation

Table 2: Solicited adverse events

Type	Event
Local AEs (immunisation site)	Discomfort Redness Swelling (soft) Induration (hard) Blisters
Systemic Clinical AEs	Abnormally raised temperature Chills Myalgia/flu-like general muscle aches Malaise (excess fatigue) Headache Nausea Vomiting
Systemic Laboratory AEs	Abnormalities in: Creatinine, AST, ALT, alkaline phosphatase, total bilirubin, glucose, Hb, total WCC, neutrophils, lymphocytes, platelets

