4.8. Subgroup Analysis

No subgroup analysis has been planned for this study.

A. Tables

Table 1 Doses received

Week	Group		
	ID/EP N=	IM/EP N=	IM/ID/EP N=
0	n (%)	n (%)	n (%)
4	n (%)	n (%)	n (%)
8	n (%)	n (%)	n (%)
20	n (%)	n (%)	n (%)

Table 2 Primary safety outcome, grade 3+ local or systemic solicited adverse event, or any event leading to treatment discontinuation.

	ID/EP (N=)	IM/EP (N=)	IM/ID/EP (N=)	Total (N=)
Participants with ≥ 1 event	n(%)	n(%)	n(%)	n(%)
Events per participant				
0	n			
1	n			
2	n			
3	n			
4	n			
≥ 5	n			
Total number of events	N	N	N	N
Type of event				
solicited local	n(%)			
solicited systemic	n(%)			
systemic	n(%)			
laboratory				
Grade of event				
1	n(%)			
2	n(%)			
3	n(%)			
4	n(%)			
Relationship to vaccine				
Definite	n(%)			
Probable	n(%)			
Possible	n(%)			
Unlikely	n(%)			
None	n(%)			

Description of any grade of local safety endpoints and any that lead to discontinuation of the vaccine regimen.

Table 3 Secondary safety outcome, AE local to injection site, within 7 days

	ID/EP	IM/EP	IM/ID/EP						
	Vaccine number								
	1	2	3	1	2	3	1	2	3
Total events									
Participants with ≥ 1 event									
Grade of event									
1									
2									
3									
4									

Table 4 Number of Solicited Adverse Events, by vaccination number

	ID/EP	IM/EP	IM/ID/EP						
	Vaccine number								
	1	2	3	4	1	2	3	4	
Total									
0									
1									
2									
3									
4									
≥ 5									
Per participant									
1									
2									
3									
4									
Per grade									
1									
2									
3									
4									

Table 5 Solicited adverse events, by type, grade and vaccination number

a) Local adverse event

Symptom	Maximum Grade	Group							
		Vaccination Number				n = number at risk			
		1 N=	2 N=	3 N=	4 N=	1 N=	2 N=	3 N=	4 N=
Discomfort	1								
	2								
	3								
	4								
Redness	1								
	2								
	3								
	4								
Swelling (soft)	1								
	2								
	3								
	4								
Induration (hard)	1								
	2								
	3								
	4								
Blisters	1								
	2								
	3								
	4								

b) Systemic adverse event

Symptom	Maximum Grade	Group							
		Vaccination Number				n = number at risk			
		1 N=	2 N=	3 N=	4 N=	1 N=	2 N=	3 N=	4 N=
Temperature	1 2 3 4								
Chills	1 2 3 4								
Myalgia	1 2 3 4								
Malaise	1 2 3 4								
Headache	1 2 3 4								
Nausea	1 2 3 4								

c) Systemic laboratory AEs

Symptom	Maximum Grade	Group							
		Vaccination Number				n = number at risk			

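### Laboratory events are primary safety events graded on numeric cut-offs, but Protocol 8.1 lets unblinded investigators decide whether an out-of-range result is reported, and the SAP does not say which source feeds the analysis

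*Protocol*

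**What the plan says.** **Laboratory abnormalities are solicited events.** Protocol section 7.4 says of solicited events: "These include disturbances in routine laboratory parameters". Table 2 lists 11 analytes: creatinine, AST, ALT, alkaline phosphatase, total bilirubin, glucose, Hb, white cells, neutrophils, lymphocytes and platelets. On capture, 7.4 says: "In addition systemic laboratory adverse events will be collected through routine laboratory testing according to the schedule". It adds that they go on the relevant CRF page and that solicited events are graded "according to the study specific toxicity table". Appendix 2 gives numeric limits for all 11; grade 3 AST or ALT, for example, is ">5.0 – 10.0 x ULN".

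**They count in the primary endpoint.** Protocol 10.2.1.1 and SAP 3.1.1 include "Grade 3 or above systemic clinical and laboratory solicited adverse event". A further primary component can take in milder laboratory events: "Any grade of adverse event within 7 days of receiving intradermal and standard intramuscular vaccinations with or without electroporation". SAP appendix Table 5, part "c) Systemic laboratory AEs", tabulates each analyte by maximum grade, 1 to 4.

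**Section 8.1 sets a reporting test.** For a result outside the local normal range, the investigator weighs four criteria when deciding whether it is an adverse event: accompanying symptoms; a need for further tests or medication; a delay or end to dosing; or, fourth, "The investigator considers the result to constitute an adverse event for any other reason". Grade is not among them, and Table 2 analytes are not exempted.

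**Who decides.** Protocol 5.2 says clinical staff know the allocation. Protocol 10.4.4 has the Clinical Investigators grade all safety endpoints.

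**The concern.** Two routes lead to a laboratory adverse event. Under 7.4 the sample is taken on schedule and the value is graded against fixed limits. Under 8.1 a clinician first decides whether the result is an event at all. Numeric limits settle the grade of an event; they do not settle whether a result becomes one. Neither document says which route takes precedence for Table 2 analytes, and neither SAP 3.1.1 nor Table 5c names its source.

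If 8.1 governs, a silent abnormality can drop out of a primary component at the discretion of someone who knows the arm. The proportions in SAP 4.5.1, their intervals and the pairwise comparisons would then rest partly on reporting habit, and the completeness of Table 5c would be unknown. Reporting also fixes reaction status, since 8.1 automatically classes a solicited event starting within 7 days of vaccination as an adverse reaction.

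**Working it through.** **1. The data flow.**
- Protocol 1.1.8 lists what the CRF data will include. Solicited events, non-solicited events, pregnancy tests and concomitant medication are named; laboratory values are not. The list may not be exhaustive.
- Protocol 11.1 keeps blood results as paper copies in the medical notes, and has a clinician mark each abnormality as clinically significant or not.
- Section 7.4 sends laboratory adverse events to the CRF. It does not say that every value goes there.

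So no section states that the trials unit receives the values from which grades could be derived.

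**2. Which grades are exposed.** A silent grade 1 or 2 value need not meet any of the first three 8.1 criteria, so its reporting turns on the fourth. A silent grade 3 or 4 value is less exposed. Protocol 6.1.5 and 7.5 refer to laboratory events confirmed on repeat testing, and a repeat test would probably meet the criterion on further tests. That is an inference, because no section requires every such value to be reported.

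**3. Number of results subject to the rule.** Protocol 7.1 schedules routine bloods at enrolment and at weeks 1, 4, 5, 8, 9, 20, 21 and 22. Table 5, footnote 5, places immunisation after the other visit procedures, so week 0 is pre-dose; SAP 4.2 makes it the baseline. That leaves 8 post-dose draws.

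- Per participant: 8 draws x 11 analytes = 88 results.
- For 24 participants: 88 x 24 = 2112 results.

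The documents give no out-of-range rate. Assuming a share *q* of results is out of range:

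| *q* (assumed) | 2112 x *q* |
|---|---|
| 1% | about 21 |
| 2.5% | about 53 |
| 5% | about 106 |

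These are results needing an 8.1 decision, not graded events. Appendix 2 grades can start beyond the normal limit; AST and ALT grade 1 starts at 1.25 x ULN.

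**4. Effect on an arm of 8.** SAP section 4 uses the Wilson interval:

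[p + z²/(2n) ± z·√(p(1−p)/n + z²/(4n²))] / (1 + z²/n), with z = 1.96.

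- x = 0, n = 8: the lower limit is 0 and the upper limit is z²/(n + z²) = 3.84/11.84 = 32.4%.
- x = 1, n = 8: centre (0.125 + 0.240)/1.480 = 0.247; half-width 1.96 x √(0.01367 + 0.01501)/1.480 = 0.224; interval 2.2% to 47.1%.

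Both agree with SAP Table 3 (0-32% and 2-47%). One participant reported or not therefore moves the estimate from 0% to 12.5% and the upper limit from 32% to 47%.

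**5. Effect on the group comparison.** Two-sided Fisher's exact p-values at 8 versus 8:

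| Events | p |
|---|---|
| 0 v 1 | 1.000 |
| 0 v 4 | 0.077 |
| 0 v 5 | 0.026 |
| 1 v 5 | 0.119 |
| 1 v 6 | 0.041 |

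The SAP states no significance level. Taking 0.05 as an assumption, one reclassified participant crosses it only when the arms already differ by four or five participants.

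**The case against.** The strongest reply is that 7.4 is a specific rule for solicited events and 8.1 a general definition covering any out-of-range parameter, so the specific rule should prevail. Section 7.4 does provide for scheduled testing, CRF recording and grading by fixed limits. This is a natural reading, and it is why the point is an unreconciled conflict and not a demonstrated loss of data. But 8.1 contains no carve-out, and the SAP does not adopt either reading.

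There are also safeguards. Protocol 11.1 requires laboratory reports to be signed, and 12.4 has monitoring check CRF entries against source. These leave an auditable record, but they do not turn an unreported value into an endpoint event.

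Third, the trial disclaims confident group comparisons (Protocol 10.3, SAP 2.2), and step 5 shows that p-values rarely turn on one participant. That stands, so the effect is mainly on proportions and intervals. For the any-grade component, Protocol 2.2.2.3 reports transient pain in virtually all recipients of the intramuscular device. The share of participants with any event may therefore be near its ceiling whatever happens to laboratory results. That limits the effect on that proportion, but not on Table 5c.

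A reader might go further and infer that the whole laboratory component rests on discretion, or that grade 3 values go uncounted. The documents do not support this: 7.4 can be read as automatic capture, the grades are numeric, and repeat testing would bring most grade 3 values within 8.1.

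**Conclusion.** The conflict is real and touches a primary component. Protocol 7.4, Table 2 and Appendix 2 point to scheduled capture with numeric grading. Section 8.1 allows unblinded staff to filter out-of-range results without reference to grade. The SAP does not choose between them.

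If 8.1 is applied as written, the likely losses are silent grade 1-2 values, in Table 5c and in the laboratory part of the any-grade-within-7-days component. Most grade 3 or above values would probably be reported, though this is not guaranteed. Each participant affected shifts an arm by 12.5 percentage points, for example from 0/8 (0-32%) to 1/8 (2-47%).

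This rests on reading 8.1 as covering Table 2 analytes, which the text permits but does not state. The size of any under-count cannot be estimated, because the documents give no abnormality or reporting rates. A reader might also infer that capture will differ by arm, or that Table 5c cannot be interpreted. Open-label reporting makes the first possible, but nothing shows that it will occur. The second is too strong: the table would be of unknown completeness.

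**What to change.** State in Protocol 8.1 and SAP 3.1.1 that the laboratory endpoint components and Table 5c are derived from every scheduled post-dose Table 2 result (8 draws, weeks 1 to 22), graded by Appendix 2 whatever the 8.1 decision. In addition:

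- Treat week 0 as baseline, so that pre-dose values are not counted as events.
- Show unconfirmed and repeat-confirmed grade 3 or above values separately, since Protocol 6.1.5 and 7.5 use confirmation and the endpoint wording does not.
- List investigator-reported laboratory adverse events separately.
- Leave causality with the investigator, and leave the discontinuation and stopping rules as they are.

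The cost is wording in two documents plus entry or export of laboratory values for 24-30 participants (24 planned, at most 30 exposed under Protocol section 9). The results are already held in the medical notes. Reported laboratory rates may be slightly higher, because silent abnormalities would be counted.
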